DAA	Direct-Acting Antivirals
DBS	Dried Blot Spots
DSMB	Data Safety Monitoring Board
HCV	Hepatitis C Virus
HIV	Human Immunodeficiency Virus
IMB model	Information-Motivation-Behavioural skills model
ICECREAM	Interventions to Curb hEpatitis C Reinfections Among Men who have sex with men
InPrEP project	Informal PrEP project
ITT	Intention To Treat
METC	Medical research ethics committee (MREC); in Dutch: medisch ethische toetsing commissie (METC)
MOSAIC	MSM Observational Study of Acute Infection with hepatitis C
MSM	Men who have Sex with Men
NGO	Non-Governmental Organization
OR	Odds Ratio
PP	Per Protocol
PrEP	Pre-Exposure Prophylaxis
RNA	RiboNucleic Acid
ROC	Receiver Operating Characteristic
RT	Randomized Trial
SHM	The Dutch HIV monitoring foundation (in Dutch: Stichting HIV Monitoring)
STI	Sexually Transmitted Infection
SVR	Sustained Virological Response
WHO	World Health Organization
WMO	Medical Research Involving Human Subjects Act (in Dutch: Wet Medisch-wetenschappelijk Onderzoek met Mensen
ZonMw	The Netherlands Organisation for Health Research and Development (in Dutch: Nederlandse organisatie voor gezondheidsonderzoek en zorginnovatie)

SUMMARY

Rationale: As highly effective therapy against hepatitis C virus (HCV) infection is available with rapid uptake, there is newfound optimism for HCV elimination. Nevertheless, HCV reinfections cause great concern in at risk populations, including men who have sex with men (MSM). In the Netherlands, MSM account for the majority of new HCV (re)infections. Although HCV treatment uptake is high in this group, modelling data indicate HCV elimination would not be feasible without a reduction in risk behaviour. This finding highlights the urgent need for effective interventions aimed at reducing risk behaviour and preventing reinfections in MSM.

Objective: To evaluate interventions aimed at reducing risk behaviour, and ultimately preventing HCV reinfections and onward spread of HCV.

Study design: Using a 3-arm randomised trial comparing run-in and intervention periods, we will evaluate the effect of two interventions and its combination on risk behaviour in MSM previously infected with HCV.

Study population: MSM aged 18 years or older with a history of a successfully treated or spontaneously cleared HCV infection.

Interventions: Intervention I is a targeted, online behavioural intervention developed as part of the project. Intervention II aims to increase the frequency of testing by offering an additional patient-initiated, home-based HCV RNA testing service with the use of self-sampled dried blot spots. Intervention III is a combination of intervention I and II.

Main study parameters/endpoints: From run-in and post-randomization questionnaires, we will evaluate the proportion at risk of HCV infection (as determined by the HCV-MOSAIC score) as the primary outcome. The HCV-MOSAIC risk score is calculated by summing up the beta coefficients specific to six self-reported risk factors when present: receptive condomless anal sex (beta 1.1), sharing sex toys (beta 1.2), unprotected fisting (beta 0.9), injecting drug use (beta 1.4), sharing straws during nasally-administered drug use (beta 1.0), and ulcerative sexually transmitted infection (beta 1.4). Secondary outcomes include incidence of HCV reinfection, changes in the individual risk behaviour items and changes in sexual wellbeing.

Nature and extent of the burden and risks associated with participation, benefit and group relatedness: One site visit will be required for all participants to sign the informed consent form. All further study procedures will be web-based or will take place from home. Participants will be exposed to five online questionnaires, with an interval of 6 months. The questionnaires and interventions can make participants more aware of their HCV risk, which could make participants feel at unease. However, we think this study poses negligible risk to the participants.

1. INTRODUCTION AND RATIONALE

1.1 Background

Hepatitis C Virus (HCV) infection may lead to liver inflammation, cirrhosis, liver cancer and death. HCV is a global health problem; about 71 million individuals worldwide are infected and every year, 495,000 deaths from HCV infection occur and the burden of disease continues to rise.(1-3) HCV is usually spread through blood-to-blood contact. Since 2000, outbreaks of sexually transmitted HCV infection have been reported among HIV-positive men who have sex with men (MSM). Risk factors independently associated with the acquisition of acute HCV among MSM include sexual risk behaviour (e.g. unprotected anal intercourse, unprotected fisting) and recreational drug use.(4) HIV/HCV coinfection results in an increased risk of both HCV and HIV related mortality.(5, 6) Currently, there is no vaccine available to prevent HCV infection. A small proportion (10-15%) of HIV-positive MSM will spontaneously clear the infection without treatment.(7, 8) Recent availability of highly effective oral HCV therapy (direct acting antivirals (DAA)) for HCV infection with cure rates of 95% has created optimism towards HCV elimination.

1.2 HCV in the Netherlands

The Dutch HCV epidemiological patterns are quite unique and the country seems to be in a good position for reaching elimination goals. The Netherlands is a country with one of the lowest HCV prevalence in the general population worldwide(3) with rapid uptake of interferon-free treatment since unrestricted access (i.e., no longer fibrosis stage restrictions) to DAA for all chronic HCV patients was authorized in November 2015. Hence, reaching the World Health Organization (WHO) HCV elimination goals (i.e., 90% reduction in new chronic infections, 65% reduction in mortality)(9), might be more feasible in the Netherlands than in other regions. Importantly, in contrast to other regions, over the last decade we have observed almost no acute HCV initial and reinfections among the classical HCV risk group of people who inject drugs, related to a high uptake of comprehensive harm reduction programs.(10-13) Thus, MSM are the sole group with ongoing HCV spread.

1.3 HCV among men who have sex with men

New HCV infections are typically found in HIV-positive MSM. Incidence of initial infection among HIV-positive MSM stabilized and was not markedly declining before DAA became widely available.(14-16) Since unrestricted DAA availability in November 2015, HCV incidence has been decreasing in the Netherlands.(17, 18) The incidence rate of acute HCV infection among HIV coinfected MSM in HIV care was 4.5 diagnoses per 1,000 PY in 2012,

6.6 in 2015 and 3.3 in 2017.(18) International data show diverging trends. In Switzerland and France for example, HCV incidence in MSM has remained stable or has shown an increase respectively(19, 20), since the availability of DAA's.

Of great concern is the more than ten times higher risk of reinfection when compared to initial infection; approximately one third of the MSM who successfully responded to HCV treatment acquired a reinfection within 2 years.(21, 22) A subsequent high incidence of HCV reinfection has also been observed in other high income countries in MSM who both respond to treatment or clear the infection spontaneously.(23, 24) An additional concern is the recent finding of a higher HCV prevalence (4.8%) in high risk HIV-negative MSM than previously reported.(25) These HCV mono-infected MSM applied for pre-exposure prophylaxis (PrEP) to prevent HIV infection and were infected with HCV strains already circulating among HIV-positive MSM. More recent data shows that the HCV incidence rate in HIV negative MSM on PrEP comparable is to that of HIV-positive MSM.(20, 26) Increasingly overlapping sexual networks between HIV-positive and HIV negative MSM(27, 28) might put these HIV-negative MSM also at risk of HCV reinfection and spread to the larger population of HIV-negative MSM cannot be excluded.

1.4 HCV treatment

The rapid uptake of DAA might contribute to HCV elimination. In the favourable Dutch epidemiological setting, targeting HIV/HCV coinfected patients, of whom 69% are MSM(29), is a logical first step towards elimination as an estimated 90% of all HIV-positive persons living in the Netherlands are regularly seen in HIV care.(18) It is promising that 15 months after broadening access of DAA therapy to all HIV/HCV-coinfected patients independent of fibrosis stage, 82% of 1471 HIV/HCV coinfected patients in the Netherlands had either achieved a sustained virological response (SVR12) or were currently still on DAA therapy.(29, 30) Treatment uptake and cure rates were highest in MSM.(29) However, modelling data indicate that even in a setting with high DAA uptake among MSM, HCV elimination would not be feasible without a reduction in risk behaviour.(31, 32) This reduction could be difficult to achieve as it might be that the new highly effective and well-tolerated treatments result in a decreased perceived threat of HCV, especially in those successfully treated with DAA and at risk of HCV reinfection. An increase in risk behaviour could likely surface and counteract treatment benefits.(33) Data indicate that MSM successfully treated with DAA are still at substantial risk of HCV reinfection.(34) This and the costs related to treatment of (re)infections highlight the urgent need for effective interventions aimed at reducing risk behaviour and preventing reinfections among MSM.

1.5 Interventions to prevent HCV reinfection

Effective interventions to prevent HCV reinfection targeting MSM are lacking. To our knowledge, behavioural interventions aimed at reducing risk behaviour for HCV transmission in MSM have only been studied within the Swiss HCVree trial.(35) Preliminary results indicated that adding a behavioural intervention to HCV treatment was feasible(36), however the results on behavioural outcomes have not been published yet. The behavioural intervention reported by the Swiss was offered to HIV/HCV co-infected MSM with inconsistent condom use and occasional sex partners, and accompanied the treatment phase of the study.(37) Participants received four 45-minutes individual sexual risk counselling sessions, assisted by an interactive online tool (n=51). This intervention was an adaptation of a previous European randomized multi-center study targeting safer sex in HIV-positive MSM(38) In this randomized controlled trial, the intervention showed short-term effectiveness in HIV-positive MSM; condom use at last intercourse increased more among intervention than control participants at 3 months follow-up (odds ratio of 3.83; 95% confidence interval 1.15 to 12.76, $P = 0.03$), but not significantly at 6 months follow-up. In addition to behavioural interventions focusing on inconsistent condom use (such as the Swiss HCVree trial), effective behavioural interventions targeting the wider range of HCV-related risk behaviours are urgently required for MSM at risk for HCV reinfection.

Additionally, more frequent testing for HCV might have the potential to change behaviour. Infection status notification can lead to a reduction in risk behaviour, as has been demonstrated for positive HIV and HCV test results.(39-42) There has been relatively little evidence about the effect of receiving a negative test result. Studies evaluating the effect of testing HIV-negative in MSM have found heterogeneity in how individuals respond to a negative test.(43, 44) There is some evidence that (repeated) negative testing may increase sexual risk behaviour.(43, 45-47) On the other hand, more frequent testing could lead to earlier detection of HCV reinfection and early treatment. Early treatment reduces the duration that reinfected patients may transmit HCV to their sex partners, hereby preventing new HCV infections on a population level.(32) Notably, home-based testing using dried blot spots (DBS) offers advantages for HCV testing, as it has shown to increase convenience, anonymity, perceived control over the testing procedure, patient autonomy and control over the own health.(48)

This project will set up, offer and evaluate two interventions (i.e. an online behavioural intervention and a home-based HCV testing intervention), alone or in combination, and possibly contribute to halting HCV transmission to the wider community of HIV-positive and HIV-negative MSM.

2. OBJECTIVES

Primary Objective:

To investigate whether the online behavioural and testing intervention, alone or in combination, causes a reduction in at risk behaviour compared to the run-in period (see [Chapter 7.1.1](#))

Secondary Objective:

To evaluate the impact of the behavioural and testing intervention, alone or in combination, on reinfection incidence, STI incidence, individual HCV related risk behaviour items and sexual wellbeing. Furthermore, we will evaluate the impact of the interventions on reinfection incidence and onward transmission using mathematical modelling.

3. STUDY DESIGN

We will perform a multi-center 3-arm randomized trial (RT) evaluating the effect of an online behavioural intervention, a home-based testing intervention, or a combination of both on HCV risk behaviour (**Figure 1**). The trial will start with a 6 month run-in period (standard care). This 6 month run-in period is used to determine at-risk behaviour under no intervention. Including a control comparator arm with no intervention was deemed unappealing to MSM (personal communication, [name], Soa Aids Nederland (NGO)) and could lead to high attrition rates. Hence, we decided that the risk of non-differential loss to follow-up would outweigh any benefit with using a control arm and we opted for a run-in comparison period instead. The intervention period will start at month 6 of the study period. Participants will be randomly assigned to one of the three arms (1:1:1 randomization). During this period, participants will receive standard care plus one or both interventions. Follow-up in the intervention period will end after 18 months. In total, five questionnaire measuring risk behaviour over the past period will be offered online every 6 months in the run-in period and intervention period (i.e., at month 0, 6, 12, 18 and 24 of the study period). This study will be viewed as a pilot approach to evaluate, within each arm, if a significant decrease in at-risk behaviour can be observed during the intervention period.

[figure not shown]

Figure 1: Study design of the ICECREAM study

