4.4 Sample size calculation

We aim to have a minimum of 78 MSM per arm (total: 234). Assuming a drop-out rate of a maximum 5% in the run-in period (based on our experience with ongoing studies), we aim to enrol 246 MSM in total (see [Figure 1](#)). As we have no initial data on the effects of our interventions, we simulated power under varying conditions of at risk behaviour during the run-in period and absolute risk reduction during the intervention. With a sample size of 78 in each arm, we would have 80% power to demonstrate a statistically significant difference, at a type 1 error of 0.05, of a >22% reduction in the primary end-point from a 60% baseline prevalence of MSM identified as at risk (HCV-MOSAIC score ≥ 2.0 , see [Chapter 9.1](#)). When

testing for differences in reduction of the primary end-point between two intervention arms (**Chapter 9.1**), while additionally assuming a 10% reduction in the comparator arm, we would have 80% power to demonstrate a statistically significant difference if a reduction of 0.43 was observed in the other intervention arm.

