5.3 Arm III: behavioural and home-based testing intervention combined

The third arm combines the behavioural intervention with the testing intervention. In this arm, both interventions will be offered to participants for 18 months. We hypothesize that the combined intervention will lead to the greatest reduction in risk behaviour. Additional testing can have different effects on risk behaviour, as described in **Chapter 1.4**. However, there is no data available on the effect of additional HCV testing among men who have sex with men that can support our hypothesis. Nevertheless, we believe that the testing intervention in combination with the behavioural intervention can increase awareness around HCV and possibly reduce risk behaviour the most.

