9. STATISTICAL ANALYSIS

9.1 Primary study parameter(s)

The primary outcome is the proportion at risk of HCV infection (as determined by a HCV-MOSAIC score ≥ 2.0) during the run-in versus intervention periods. The score is calculated by summing up the beta-coefficients specific to six self-reported risk factors when present in the previous 6 months (see [Chapter 7.1.1](#)). The HCV-MOSAIC risk score has been previously validated for acute (primary) HCV-infection in HIV-positive MSM and the optimal cut-off to predict HCV positivity was defined at ≥ 2.0 .(65) In addition, we recently evaluated whether the risk score could also identify individuals at high-risk of HCV reinfection, showing comparable performance (The Area Under the ROC Curve = 0.76) to that of primary acute HCV-infection.(66)

The six items of the HCV-MOSAIC risk score will be obtained using the answers from the study questionnaire every six months. The proportion achieving the primary outcome will be summarized at month 6, 12, 18 and 24 visits within each study arm. The probability of the primary outcome will be compared between the run-in (month 6) and intervention periods (month 12, month 18, month 24) using a mixed-effect logistic regression model. In this model, each individual will serve as their own control and between-individual differences at baseline will be accounted for using a random-intercept. Pre versus post-intervention odds ratios (ORs) and their 95% confidence intervals (CI) will be estimated and stratified on study arm, allowing us to identify interventions with significant differences. No multivariable adjustments will be applied. Additional analysis will be conducted in which ORs between arms will be compared by including and testing an interaction term between period and arm in the model (two arms at a time, for a possible three comparisons). No *p*-value adjustments will be made for multiple comparisons to avoid unnecessary correction on the possibly underpowered test for interaction.(67)

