3.5.5. Differences in HCV-MOSAIC risk scores between arms

- **Definition**

The proportion of participants achieving an HCV-MOSAIC risk score ≥ 2.0 at the end of follow-up, compared between intervention arms.

ORs comparing arms and 95%CI are calculated.

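### The two randomised contrasts that isolate each intervention (arm III v II, arm III v I) are planned only as undirected extras, while each arm's primary conclusion rests on a before-after comparison with the run-in

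*Protocol*

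**What the plan says.** - **Comparator.** Protocol section 3 considered a no-intervention arm unappealing to participants, and concluded that the risk of loss to follow-up "would outweigh any benefit with using a control arm and we opted for a run-in comparison period instead". Protocol section 2 asks whether the interventions, alone or in combination, cause a reduction compared with the run-in. SAP 2.1.1 defines the primary comparison as run-in against intervention period within each arm.
- **Arms.** Allocation is 1:1:1 at M6. Arm I receives the behavioural intervention and arm II home-based testing. "The third arm combines the behavioural intervention with the testing intervention" (protocol 5.3), and the same section hypothesises that the combination will reduce risk most.
- **Between-arm analysis, protocol.** Section 9.1 adds a test of the period-by-arm interaction, "two arms at a time, for a possible three comparisons". The intervention period there covers M12, M18 and M24. Section 4.4 gives a power statement for this test, and 9.2 says that outcomes will also be compared across arms.
- **Between-arm analysis, SAP.** Sections 2.1.2 and 3.5.5 make it a secondary endpoint: the proportion with a score of at least 2.0 "at the end of follow-up, compared between intervention arms". No pair is named. SAP 2.2.2 fits an arm-by-time interaction but tests time points only within arms. SAP 1.4 has no between-arm power statement.

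**The concern.** A before-after contrast attributes to the intervention everything that changes between the run-in and month 24. The documents give reasons to expect change: SAP 3.3.3 records the influence of COVID-19 measures and mpox on sexual behaviour, and protocol 4.1 expects condomless anal sex to keep rising as PrEP use grows. A downward trend could produce a significant fall without any effect; an upward trend could hide a real one.

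The randomised arms already contain a comparison in which a trend common to all arms cancels. Arm III differs from arm II only by the behavioural intervention, and from arm I only by testing. Neither document gives these pairs that role. I v II, listed on equal terms in protocol 9.1, compares two strategies and tests neither against its absence. By looking only at the end of follow-up, the SAP also leaves M12 and M18 out of the between-arm answer. And no planned test is tied to the protocol 5.3 hypothesis that the combination does best, which III v I and III v II would address.

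**Working it through.** **1. The plan's own figure.** Protocol 4.4: "We aim to have a minimum of 78 MSM per arm (total: 234"); "we would have 80% power to demonstrate a statistically significant difference, at a type 1 error of 0.05", for a fall of more than 22% in the "reduction in the primary end-point from a 60% baseline prevalence of MSM identified as at risk". The effect scale is absolute (power was simulated over "varying conditions of at risk behaviour during the run-in period and absolute risk reduction during the intervention"). For two independent proportions, 0.60 and 0.38, two-sided 0.05, mean 0.49:

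n = [1.96·√(2·0.49·0.51) + 0.842·√(0.60·0.40 + 0.38·0.62)]² / 0.22² = 79.9, so 80 per arm. At 78 the power is 79.1%. The figure reproduces.

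The formula is for two independent groups, so 78 per arm also gives about 80% power for a III v II or III v I difference of about 22 points at a single visit.

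Protocol 4.4 separately says that the interaction test has 80% power for a reduction of 0.43 against 10% in the comparator, a gap of 33 points if both are absolute. A difference-in-differences of independent proportions gives 88% for that gap, and reaches 80% at a reduction of about 0.40. The simulation settings are not given, so I do not call this an error.

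**2. What a time trend does to the within-arm contrast.** Assumptions, none of them in the documents: no intervention effect, 60% at risk at M0, linear drift of d points per visit, exchangeable between-visit correlation r, and variance 0.25 per observation.

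- Reference M0 and M6 (SAP 2.2.2): shift = 2.5d; SE = √[0.25(1−r)(1/3 + 1/2)/78] = 4.3 points at r = 0.3, 3.7 at r = 0.5.
- Reference M6 only (protocol 9.1): shift = 2d; SE = √[0.25(1−r)(1/3 + 1)/78] = 5.5 and 4.6 points.
- Chance of a significant fall ≈ Φ(shift/SE − 1.96), taking a fall as positive.

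| Assumed drift per visit | M0 and M6 reference | M6 reference |
|---|---|---|
| 3 points down | 41 to 54% | 19 to 25% |
| 1 point down | 8 to 10% | about 6% |
| 3 points up | about 0% | about 0% |

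With no drift the nominal rate in this direction is 2.5%. Simulating 4,000 trials per scenario at 3 points down gave 42 to 54% and 19 to 26%; III v II over M12 to M24 rejected (two-sided) in 5 to 6%. With 3 points up, the shift of 2.5 × 3 = 7.5 points would cancel a true reduction of that size under the SAP reference.

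**3. Precision of the two contrasts.** 78 per arm, no dropout, proportion near 0.5, linear approximation. Detectable difference at 80% power = 2.8·√(2V/78), where V is the per-person variance:

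- Run-in adjusted: V = 0.25(1+2r)/3 − (0.25r)²/[0.25(1+r)/2]
- Difference-in-differences, M0 and M6 reference: V = 0.25(1−r)(5/6)
- M24 only, unadjusted: V = 0.25

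| Analysis | r = 0.3 | r = 0.5 | r = 0.7 |
|---|---|---|---|
| M12–M24, run-in adjusted | 14.1 | 12.9 | 10.6 |
| M12–M24, difference-in-differences | 17.1 | 14.5 | 11.2 |
| M24 only, unadjusted | 22.4 | 22.4 | 22.4 |

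The SAP 2.2.2 model has no run-in covariate, so a change contrast taken from it as written corresponds to the second row. With M6 alone as reference, that row becomes 21.7, 18.3 and 14.2. Relative to the within-arm SE, the difference-in-differences SE is √2 = 1.41 times as large at every r; the adjusted SE is 1.16, 1.26 and 1.34 times.

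**The case against.** **Between-arm comparisons are planned.** A reader might infer that each intervention is judged only against the run-in. The documents contradict this: protocol 4.4, 9.1 and 9.2 and SAP 2.1.2 and 3.5.5 all provide for comparing arms, and the three pairs in 9.1 include III v II and III v I over the whole intervention period. The loss of M12 and M18 is confined to the SAP endpoint. What stands is rank and direction: the pairs are never identified as the randomised estimates of each component.

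**The low rank was disclosed.** The protocol calls the trial a pilot and its interaction test possibly underpowered. That is fair, and the contrasts remain imprecise. But low power is a reason for wide intervals, not for leaving the contrasts unnamed.

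**The contrasts answer a different question.** It is tempting to say that every causal claim should rest on them. The documents do not support that. Protocol section 2 defines the objective against the run-in, for the interventions alone or in combination, whereas III v II and III v I give only the increment over the other intervention. Protocol 1.5 notes that repeated negative tests may increase risk behaviour, so interaction between the components is plausible. Moving all claims to these contrasts would replace the stated estimand. This objection stands.

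**The drift is assumed.** One could read the 41 to 54% as the trial's false-positive rate. It is not: the documents give no drift, the one direction they state is upward, and the rate falls to nearly zero under an upward trend. What stands is that the contrast is exposed in both directions.

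**Conclusion.** The point holds as one of labelling and use of data. The primary conclusion for each arm cannot separate an intervention effect from a time trend. The concurrent randomised contrasts that can are present, but are ranked as additional or secondary, are not distinguished from I v II, and in the SAP are limited to the end of follow-up.

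Using M12 to M24 lowers the detectable difference from about 22 points to about 14 to 11 with run-in adjustment, or 17 to 11 without it. This rests on 78 per arm, no dropout, a proportion near 0.5 and an assumed correlation of 0.3 to 0.7. Counting men lost to follow-up as at risk, as the SAP's ITT rule does, would dilute the contrasts. Randomisation removes a common time trend; it does not remove reporting differences in an unblinded trial with self-reported outcomes. The gain is thus mainly in validity, with a useful gain in precision over M24 alone. It is an improvement that should be made, not evidence that the planned primary analysis is unusable.

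**What to change.** In SAP 2.1.2, 2.2.2 and 3.5.5:

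1. Name two contrasts in advance as the concurrent randomised estimates: III v II (behavioural intervention added to testing) and III v I (testing added to the behavioural intervention). Keep I v II as a comparison of strategies.
2. Estimate both over M12 to M24 with 95% CIs from the joint arm-by-time model. Either add the M0/M6 run-in level as a covariate, with only post-randomisation visits as outcomes, or keep the run-in visits as outcomes and constrain their means to be equal across arms. Keep the M24 comparison as supportive.
3. Keep the within-arm run-in contrast as the stated primary analysis. Report the two contrasts beside it, and state that a within-arm fall alone does not separate the intervention from a time trend.
4. State that the two contrasts carry no multiplicity adjustment. At 5% each the chance of at least one false positive would be 1 − 0.95² = 9.75% if they were independent; they share arm III, so this is approximate.

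The cost is SAP wording and two contrast statements, with no new data or participants. The drawbacks are that the effects are conditional on the other intervention and estimate neither intervention alone nor the combination against nothing, that the SE exceeds the within-arm SE, and that averaging over visits can mask waning, which is why the visit-specific estimates should be shown as well.
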